2.1.3 Cohort 3 Inclusion and Exclusion Eligibility Criteria

Inclusion Criteria

- 2.1.3.1 Age 12 to 26 years
- 2.1.3.2 Females and males
- 2.1.3.3 HIV-negative
- 2.1.3.4 Patients \geq 18 years willing to provide informed consent or parent/guardian willing to provide informed consent for minor children <18 years of age.
- 2.1.3.5 Informed assent for patients 12-17 years of age (Optional at the discretion of the Principal Investigator and Parent/Guardian based on maturity level of minor)

2.1.3.6 Willing to use acceptable forms of contraception, if applicable, or abstinence to prevent pregnancy.

Exclusion Criteria

2.1.3.7 Any of the following hematologic abnormalities:

2.1.3.7.1 Hemoglobin < 10.0 g/dL

2.1.3.7.2 Neutrophil count < 1500/mm³

2.1.3.7.3 Platelet count < 75,000/mm³

2.1.3.7.4 PT or PTT \geq 1.5X ULN (with the exception of patients with known clotting disorders or known lupus anticoagulant).

2.1.3.8 Any of the following hepatic abnormalities

2.1.3.8.1 ALT/SGPT and/or AST/SGOT > 2.5X ULN

2.1.3.8.2 Total Bilirubin > 1.5X ULN unless attributable to protease inhibitor therapy.

2.1.3.9 Positive tests (antibody and/or antigen) for HIV, hepatitis B and hepatitis C viruses, unless the result is consistent with prior vaccination or prior infection with full recovery.

2.1.3.10 Acute infection requiring therapy at time of enrollment. Participants may be eligible for study after being on stable and appropriate anti-infective therapy.

2.1.3.11 Chemotherapy for active cancer.

2.1.3.12 Pregnancy or breastfeeding

2.1.3.13 Use of immunosuppressive or immunomodulating agents within 8 weeks prior to study enrollment. Note: patients receiving oral corticosteroids for management of asthma or contact hypersensitivity for \leq 14 days in duration will be allowed to enroll as long as it has been \geq 30 days since oral corticosteroid administration.

2.1.3.14 Known immediate hypersensitivity to yeast or any of the vaccine components.

2.1.3.15 Use of investigational agents within 4 weeks prior to study enrollment.

2.1.3.16 Active external genital warts requiring treatment or CIN 2/3.

2.1.3.17 Any clinically significant diseases or findings during study screening that, in the opinion of the Principal Investigator or Lead Associate Investigator may interfere with the study.

2.2 RESEARCH ELIGIBILITY EVALUATION

Protocol screening evaluation will be performed within 14 days of starting HPV vaccination and will include a complete history, review of systems and physical examination with documentation of abnormalities.

2.2.1 Screening Studies

2.2.1.1 HIV serology

2.2.1.2 Hepatitis B serology: anti-HepB S, HepB S ag

- 2.2.1.3 Hepatitis C serology: anti-HCV
- 2.2.1.4 CBC with differential, platelets and reticulocyte count
- 2.2.1.5 PT, PTT
- 2.2.1.6 Acute panel
- 2.2.1.7 Hepatic panel
- 2.2.1.8 Mineral panel
- 2.2.1.9 Lipid panel
- 2.2.1.10 Amylase, lipase
- 2.2.1.11 Quantitative Immunoglobulins and IgG subclasses
- 2.2.1.12 Urinalysis
- 2.2.1.13 VDRL
- 2.2.1.14 Serum pregnancy test in post-menarchal females
- 2.2.1.15 EKG
- 2.2.1.16 Chest x-ray
- 2.2.1.17 CD4 percent and absolute cell count (for HIV-infected patients)
- 2.2.1.18 HIV-1 RNA levels by RT PCR (for HIV-infected patients)
- 2.2.1.19 Gynecologic evaluation, cervical cytology (Pap smear) and HPV DNA testing (performed on sexually active females only)

2.3 PATIENT REGISTRATION AND TREATMENT RANDOMIZATION

This is a non-randomized study. Candidate screening will be carried out using NCI protocol 01-C-0129 “Eligibility Screening and Tissue Procurement for the National Cancer Institute (NCI) Center for Cancer Research (CCR) Clinical Protocols”. Following eligibility screening, each patient will be discussed with the Principal Investigator or the Lead Associate Investigator. If they are found to be eligible, the patient and their guardian (if applicable) will be presented with a detailed description of the study protocol plan and treatment. The specific requirements, objectives, risks, alternatives, time commitments and potential benefits will be reviewed with the patient and guardian (if applicable). The Informed Consent (patients \geq 18 years or parent/legal guardian of patients $<$ 18 years) and Informed Assent (patients 12-17 years) document(s) will be given to the patient and their guardian (if applicable) which they will be asked to review and ask questions about prior to agreeing to participate in the protocol. The patient will be reassured that participation on this trial is entirely voluntary and that they may withdraw or decide against receipt of vaccination at any time without adverse consequences. The Principle Investigator or their designee is responsible for obtaining a signed statement of informed consent (and assent if the patient is 12-17 years of age) approved by the IRB. A Confirmation of Eligibility Checklist must also be completed and submitted via FAX ([contact]) or by internet/intranet to the Central Registration Office between the hours of 8:30am – 5:00pm, Monday through Friday. No evening weekend or holiday registrations will be permitted. Patients must be registered within 24 hours of signing the consent document. Once eligibility is confirmed and the patient is registered, The Central Registration Office will FAX a confirmation of the registration to the PI and will also confirm the

patient registration with the Clinical Center Investigational Drug Pharmacy. Patient study numbers will be assigned as follows:

- Cohort 1 (HIV-infected on HAART): study numbers 101-135
- Cohort 2 (HIV-infected, on no therapy): study numbers 201-235
- Cohort 3 (HIV-negative controls): study numbers 301-335.

The Central Registration Office will also be notified if a patient is taken off protocol- either due to study withdrawal or study completion. This study does not involve any treatment randomization.

3 STUDY IMPLEMENTATION

3.1 STUDY DESIGN

This is a non-randomized, prospective, phase I study of the quadrivalent human papillomavirus (types 6, 11, 16, 18) recombinant vaccine. The vaccine is a non-infectious recombinant, vaccine prepared from highly purified VLPs of the major capsid (L1) protein of HPV types 6, 11, 16 and 18.⁷⁹ The vaccine was approved and licensed by the FDA for clinical use on June 8, 2006. The study includes 3 cohort populations:

- Cohort 1: HIV-infected patients receiving stable HAART therapy
- Cohort 2: HIV-infected patients on no antiretroviral therapy
- Cohort 3: HIV-negative, healthy, age- and gender-matched controls

The study is designed to determine the safety and immunogenicity of this recombinant vaccine in pre-adolescents, adolescents and young adults with HIV infection who are at increased risk of HPV co-morbidity because of their HIV disease. Since HPV co-morbidity has been documented in both HIV-infected men and women, the vaccine will be administered to both males and females in this study. A cohort of healthy, age-matched control patients will allow comparison of safety and immunogenicity endpoints between HIV-negative and HIV-positive study subjects. The study design will also permit comparison of immunogenicity between HIV-infected patients on HAART and those not receiving antiretroviral treatment. Oral/buccal and anogenital sampling for HPV DNA will be performed on all study subjects to allow cross-sectional characterization of HPV DNA positivity in the study cohort populations. In addition, HPV and HIV knowledge and risk and sexual behaviors will be assessed in all study subjects. Total study duration is 4 years.

Study subjects will be recruited through dissemination of protocol information and eligibility criteria to pediatric and adolescent HIV clinical programs in the Baltimore/D.C. Metropolitan area including the University of Maryland, Johns Hopkins University, Children's National Medical Center, Howard University Hospital, and Georgetown Hospital. In addition to web-based dissemination of information (www.ClinicalTrials.gov) protocol information will be distributed to community-based organizations serving HIV-infected children, adolescents and at-risk youth. Providers will be encouraged to refer HIV-uninfected siblings to enroll in the HIV-negative control cohort of the study. No incentives will be offered for participation in this study.

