1.2.6 Rationale for Study Cohort Population

This study will be conducted in both HIV-infected females and males 12-26 years of age. Since the risk of HPV acquisition is intensified during adolescence and young adulthood because of risk-taking and exploratory behaviors and because of the well-documented co-morbidities associated with sexually acquired HPV in individuals with HIV infection, both males and females are included in the study. It is anticipated that Cohort 1 will be comprised primarily (but not exclusively) of sexually naïve pre-adolescents and adolescents infected with HIV vertically or by transfusion early in life that have experienced successful immune reconstitution and viral load reduction on HAART therapy (i.e. CD4 count ≥ 350 cells/mm³ and HIV-1 RNA levels $\leq 20,000$ copies/ml). This population represents an ideal one to investigate vaccine immunogenicity given the high likelihood of HPV acquisition following the initiation of sexually activity.

It is anticipated that Cohort 2 will be comprised primarily (but not exclusively) of adolescents and young adults with sexually acquired HIV infection that have no current indication for HAART therapy according to current USPHS Treatment Guidelines (i.e. CD4 count ≥ 500 cells/mm³ and HIV-1 RNA levels $\leq 20,000$ copies/ml).⁹⁸ These individuals represent a unique population to assess HPV vaccine immunogenicity and safety that parallels populations in developing countries with little or no access to antiretroviral treatment where there is a high burden of prevalent HPV and HIV disease. Both Cohorts 1 and 2 will permit assessment of whether HPV vaccination is associated with alterations in HIV-1 RNA levels and if observed, whether alterations are mitigated in the presence of HAART. In addition, both HIV-infected cohorts will allow investigation of the impact of CD4 count and HIV-1 RNA levels on HPV vaccine immunogenicity.

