Cohort 3 will be comprised of HIV-negative controls (total N=35) that will allow comparative analysis of vaccine immunogenicity, duration of responses, carriage of HPV DNA in oral/buccal and anogenital samples and risk behaviors compared to the HIV-infected cohorts (total N=70). Every effort will be made to enroll HIV-negative individuals that are representative for both age and gender compared to the HIV-positive population. HIV-negative individuals will be recruited through the NIH Clinical Center's Clinical Research Volunteer Program (CRVP) for healthy volunteers [contact] / [name] or [contact]) and may also include HIV-negative siblings of HIV-infected patients. The CRVP has a well-established track record in the recruitment of both adult and pediatric/minor volunteers for NIH studies.

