2 ELIGIBILITY ASSESSMENT AND ENROLLMENT

2.1 ELIGIBILITY CRITERIA

2.1.1 Cohort 1 Inclusion and Exclusion Eligibility Criteria

Inclusion Criteria

- 2.1.1.1 Age 12 to 26 years
- 2.1.1.2 Females and males
- 2.1.1.3 HIV-positive
- 2.1.1.4 CD4 cell count and HIV-1 RNA level parameters
 - 2.1.1.4.1 CD4 cell count \geq 350 cells/mm³
 - 2.1.1.4.2 HIV-1 RNA level by RT PCR \leq 20,000 copies/ml
- 2.1.1.5 On stable HAART regimen for > 6 months with CD4 and viral load parameters as outlined in 2.1.1.4
- 2.1.1.6 Patients > 18 years willing to provide informed consent or parent/guardian willing to provide informed consent for minor children <18 years of age.
- 2.1.1.7 Informed assent for patients 12-17 years of age (Optional at the discretion of the Principal Investigator and Parent/Guardian based on maturity level of minor)
- 2.1.1.8 Willing to use acceptable forms of contraception, if applicable, or abstinence to prevent pregnancy.

Exclusion Criteria

- 2.1.1.9 Any of the following hematologic abnormalities
 - 2.1.1.9.1 Hemoglobin < 10.0 g/dL
 - 2.1.1.9.2 Neutrophil count < 1500/mm³
 - 2.1.1.9.3 Platelet count < 75,000/mm³
 - 2.1.1.9.4 PT or PTT \geq 1.5X ULN (with the exception of patients with known clotting disorders or known lupus anticoagulant).
- 2.1.1.10 Any of the following hepatic abnormalities

- 2.1.1.10.1 ALT/SGPT and/or AST/SGOT > 2.5X ULN
- 2.1.1.10.2 Total bilirubin > 1.5X ULN unless attributable to protease inhibitor therapy.
- 2.1.1.11 Positive tests (antibody and/or antigen) for hepatitis B and hepatitis C viruses, unless the result is consistent with prior vaccination or prior infection with full recovery.
- 2.1.1.12 Acute infection requiring therapy at time of enrollment. Participants may be eligible for study after being on stable and appropriate anti-infective therapy.
- 2.1.1.13 Chemotherapy for active cancer.
- 2.1.1.14 Documented history of non-adherence to antiretroviral treatment regimen within 12 months of study entry.
- 2.1.1.15 Pregnancy or breastfeeding.
- 2.1.1.16 Use of immunosuppressive or immunomodulating agents within 8 weeks of study enrollment. Note: patients receiving oral corticosteroids for management of asthma or contact hypersensitivity for < 14 days in duration will be allowed to enroll as long as it has been > 30 days since oral corticosteroid administration.
- 2.1.1.17 Known immediate hypersensitivity to yeast or any of the vaccine components.

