2.1.2 Cohort 2 Inclusion and Exclusion Eligibility Criteria

Inclusion Criteria

- 2.1.2.1 Age 12 to 26 years
- 2.1.2.2 Females and males
- 2.1.2.3 HIV-positive
- 2.1.2.4 CD4 cell count and HIV-1 RNA level parameters
 - 2.1.2.4.1 CD4 cell count \geq 500 cells/mm³
 - 2.1.2.4.2 HIV-1 RNA level by RT PCR \leq 20,000 copies/ml.
- 2.1.2.5 *Not* receiving antiretroviral treatment with CD4 and viral load parameters as outlined in 2.1.2.4.
- 2.1.2.6 Patients \geq 18 years willing to provide informed consent or parent/guardian willing to provide informed consent for minor children <18 years of age.
- 2.1.2.7 Informed assent for patients 12-17 years of age (Optional at the discretion of the Principal Investigator and Parent/Guardian based on maturity level of minor)
- 2.1.2.8 Willing to use acceptable forms of contraception, if applicable, or abstinence to prevent pregnancy.

Exclusion Criteria

- 2.1.2.9 Any of the following hematologic abnormalities:
 - 2.1.2.9.1 Hemoglobin < 10.0 g/dL
 - 2.1.2.9.2 Neutrophil count < 1500/mm³
 - 2.1.2.9.3 Platelet count < 75,000/mm³
 - 2.1.2.9.4 PT or PTT \geq 1.5X ULN (with the exception of patients with known clotting disorders or known lupus anticoagulant).
- 2.1.2.10 Any of the following hepatic abnormalities
 - 2.1.2.10.1 ALT/SGPT and/or AST/SGOT > 2.5X ULN
 - 2.1.2.10.2 Total bilirubin > 1.5X ULN unless attributable to protease inhibitor therapy.
- 2.1.2.11 Positive tests (antibody and/or antigen) for hepatitis B and hepatitis C viruses, unless the result is consistent with prior vaccination or prior infection with full recovery.
- 2.1.2.12 Acute infection requiring therapy at time of enrollment. Participants may be eligible for study after being on stable and appropriate anti-infective therapy.
- 2.1.2.13 Chemotherapy for active cancer.
- 2.1.2.14 Pregnancy or breastfeeding.
- 2.1.2.15 Use of immunosuppressive or immunomodulating agents within 8 weeks prior to study enrollment. Note: patients receiving oral corticosteroids for management of asthma or contact hypersensitivity for \leq 14 days in duration will be allowed to enroll as long as it has been \geq 30 days since oral corticosteroid administration.
- 2.1.2.16 Known immediate hypersensitivity to yeast or any of the vaccine components.
- 2.1.2.17 Use of investigational agents within 4 weeks prior to study enrollment.
- 2.1.2.18 Active external genital warts requiring treatment or CIN 2/3.

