6.1 PRIMARY IMMUNOGENICITY ANALYSIS PART I

Does vaccine-induced antibody titer differ between study cohorts at a pre-determined primary timepoint X?

4 comparisons:

- Cohort 1 (HIV-infected, on HAART) vs. cohort 2 (HIV-infected, no HAART)
- Cohort 1 (HIV-infected, on HAART) vs. cohort 3 (healthy, HIV negative controls)
- Cohort 2 (HIV-infected, no HAART) vs. cohort 3 (healthy, HIV negative controls)
- Cohorts 1 & 2 (HIV-infected) vs. cohort 3 (healthy, HIV negative controls)

For each pairwise comparison, allowing for 4 primary comparisons as defined above among cohorts at a single time-point, we will need to plan to test with as small as a 0.0125 p value for each of the 4 comparisons in the primary analysis. With 35 vaccine recipients in each of Cohorts 1, 2 and 3, there will be at least 94% power to detect differences among cohorts as described above, of 1.0 standard deviation effect size for a single time-point.

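### Controls are described as matched but nothing in the plan matches them, and the titer comparisons specify no age or sex adjustment although the cohorts are expected to differ in age

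*Combined protocol and SAP*

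**What the plan says.** Section 3.1 lists "Cohort 3: HIV-negative, healthy, age- and gender-matched controls". The Precis, section 1.1, a later sentence of 3.1 and Appendix 11 claim matching on age only.

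The enrolment rules are the same for every cohort: "2.1.1.1 Age 12 to 26 years", "2.1.2.1 Age 12 to 26 years" and "2.1.3.1 Age 12 to 26 years", each with females and males admitted. Section 2.3 assigns study numbers by cohort, with no age band, sex quota or matching step. The only commitment on comparability is in 1.2.6: "Every effort will be made to enroll HIV-negative individuals that are representative for both age and gender compared to the HIV-positive population". Controls come from a healthy-volunteer programme and may include HIV-negative siblings.

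Section 1.2.6 also describes who is expected. Cohort 1 should be mainly pre-adolescents and adolescents infected early in life. For the other HIV cohort, "It is anticipated that Cohort 2 will be comprised primarily (but not exclusively) of adolescents and young adults with sexually acquired HIV infection". It gives no expected sex mix.

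Section 6.1 names four primary comparisons: 1 v 2, 1 v 3, 2 v 3, and 1 and 2 pooled v 3. Section 6.2 repeats them over four time-points. Neither section names an age or sex covariate or stratum. The linear mixed model in 6.2 is optional, is meant for longitudinal patterns, and lists no covariates. Section 6.4 relates titer to CD4 count and viral load only.

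**The concern.** The study is not randomised, so nothing in the design balances age or sex across cohorts. If antibody response varies with either, a difference in their distribution shifts the titer contrast, and the shift is read as an effect of HIV or of HAART. It can act in either direction: it can create a difference or hide one. Hiding a deficit matters here, because section 8.3 wants to learn whether HIV-infected people may need additional doses.

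The word matched tells the reader that this has been dealt with for the controls. Neither enrolment nor the specified analysis does so.

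**Working it through.** **1. The plan's own figures.** Inputs from 6.1 and 6.2: 35 per cohort, 1 SD difference, alpha 0.0125 (0.05/4) or 0.003. Section 6.1 does not state sidedness; two-sided is assumed, as in 6.2. For a plain two-sample t-test the noncentrality is d / sqrt(1/n1 + 1/n2), which is 4.18 for 35 v 35 and 4.83 for 70 v 35.

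| Comparison | Alpha | Stated power | Recomputed |
|---|---|---|---|
| 35 v 35 | 0.0125 | at least 94% | 94.4% |
| 35 v 35 | 0.003 | 85% | 86.0% |
| 70 v 35 | 0.003 | 96% | 96.1% |

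The stated powers are those of tests with no covariates.

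**2. Which contrasts are exposed.** Suppose 1.2.6 is right about the two HIV cohorts and the controls represent the pooled HIV-positive group (35 + 35). The under-18 share among controls then lies midway between the shares in Cohorts 1 and 2.
- Cohort 1 v 2 carries the full age gap.
- Cohorts 1 v 3 and 2 v 3 each carry about half of it, in opposite directions.
- The pooled contrast carries roughly none.

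**3. Size of a shift.** The documents give no titer by age, so both inputs are assumptions: a difference of 0.3 to 0.7 SD in log titer between under-18s and adults, and a difference of 30 to 50 percentage points in under-18 share between the two cohorts compared. The shift is their product: 0.3 x 0.30 = 0.09 SD up to 0.7 x 0.50 = 0.35 SD.

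| Shift (SD), 35 v 35, alpha 0.0125 | Rejection with no true difference | Power for a true 1 SD difference, shift opposing |
|---|---|---|
| 0 | 1.25% | 94.4% |
| 0.09 | 1.9% | 88.9% |
| 0.20 | 4.7% | 78.0% |
| 0.35 | 14.3% | 56.3% |

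If 30 to 50 points is the gap between Cohorts 1 and 2 and the controls sit midway, the control contrasts carry 15 to 25 points. Their shift is then 0.3 x 0.15 = 0.045 SD to 0.7 x 0.25 = 0.175 SD, with rejection below the 4.7% found at 0.20 SD.

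**4. Power of the adjusted test.** Age enters as under 18 v 18 and over, and sex is taken as balanced. With shares centred on 50%, the squared correlation of age group with cohort is the squared difference in shares, so variance inflation is 1/(1 - 0.09) = 1.10 at 65% v 35% and 1/(1 - 0.25) = 1.33 at 75% v 25%. The residual variance is 1 - p(1 - p)g², where p is the under-18 share and g the age effect. Two degrees of freedom are lost (68 to 66).

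| Under-18 shares | Age effect g | Residual variance | Adjusted power |
|---|---|---|---|
| 65% v 35% | 0.3 | 0.980 | 92.5% |
| 65% v 35% | 0.7 | 0.889 | 94.9% |
| 75% v 25% | 0.3 | 0.983 | 85.8% |
| 75% v 25% | 0.7 | 0.908 | 88.8% |

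In the last row the shift is 0.35 SD, so if it opposes the true difference the unadjusted test has 56% power against 89% adjusted.

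**The case against.** The strongest reply is that 1.2.6 does plan for comparability. Controls are to be representative of the HIV-positive group in age and gender, and sibling referral may bring in controls of similar age. That stands for the pooled contrast. It does not protect the two pairwise control contrasts, and it has no bearing on Cohort 1 v 2.

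Secondly, the documents nowhere say that titer depends on age or sex. Section 1.2.5 reports seropositivity of 99.5% to 99.8% across all age groups tested and gives no titers by age. This also stands: the figures above are a sensitivity range, not an estimate. Near-universal seropositivity does not show that titers are equal, however, and the same section says the male data were insufficient to assess immunogenicity.

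Thirdly, section 6.1 names no test and 6.2 allows a mixed model with unspecified covariates, so adjustment is not excluded. A reader might infer that the plan commits to unadjusted tests. That rests on silence and on the form of the power figures. What can be said is that the primary analysis leaves the choice open.

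Finally, adjustment costs power when age and cohort are strongly associated. This is correct and is a reason to restate power.

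**Conclusion.** The concern holds in a limited form. The controls are called matched without any matching procedure. The two HIV cohorts are expected to differ in age, and no age or sex adjustment is specified for the primary cohort comparisons. Cohort 1 v 2 is the most exposed, followed by 1 v 3 and 2 v 3.

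Under the assumed 0.3 to 0.7 SD age effect and a 30 to 50 point difference in under-18 share between the cohorts compared, false rejection at 0.0125 would be 1.9-14% and power against an opposing shift 89-56%, for 35 v 35. For a control contrast with the 1.2.6 aim met, a 30 to 50 point difference would require a gap of 60 to 100 points between Cohorts 1 and 2, so the upper end applies mainly to Cohort 1 v 2 or to a failed recruitment aim.

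Two stronger readings are not supported. A reader might infer that the protocol expects a sex imbalance; it gives no sex mix for any cohort, so an imbalance is only possible. A reader might also apply the same shift to the pooled 70 v 35 contrast, where rejection would reach 20% at 0.35 SD. That applies only if the effort to recruit representative controls fails.

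**What to change.** For all four cohort comparisons in 6.1 and 6.2, make the primary result the cohort difference from a linear model of log titer on cohort, age and sex. Fix the form of the age term in advance, and report the unadjusted difference as supportive.

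Restate power for the adjusted test. At 0.0125 and 35 v 35 it is about 92-95% for under-18 shares of 65% v 35% and about 86-89% for 75% v 25%, assuming a 0.3 to 0.7 SD age effect.

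Replace the age and gender matching claim in 3.1, and the age matching claim in the Precis, 1.1, 3.1 and Appendix 11, with the description in 1.2.6 ("Every effort will be made to enroll HIV-negative individuals that are representative for both age and gender"), unless a matching procedure is defined. Matching 35 controls to the two HIV cohorts combined would help the pooled contrast, but it cannot match one group to two cohorts of different age, so it does not replace the adjustment.

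The cost is some loss of power if the cohorts differ strongly in age. No new data or subjects are needed, and the analysis change can be made whether or not enrolment has finished.
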